**Project Goal**

Evaluate the impact of Ga-68 DOTATOC PET-CT on management of patients with somatostatin receptor positive tumors

## I. Introduction:

### Neuroendocrine Tumors

Neuroendocrine tumors are solid malignant tumors that arise from dispersed neuroendocrine cells found throughout the body. Gastroenteropancreatic neuroendocrine tumors (NETs) can be divided into two groups: Carcinoid tumors that may arise from the lungs, stomach, small bowel or colon and pancreatic neuroendocrine tumor. The clinical behavior of NETs is extremely variable; some may cause hormone hypersecretion and others may not, the majority of them are slow-growing tumors (well-differentiated NETs), whereas some NETs are highly aggressive (poorly differentiated NETs). The incidence of NETs is increasing, from 1.1/100,000 per year in 1973 to 5.3/100,000 per year in 2004. Among NETs, 25% have distant metastases and 25% have regional involvement at the time of initial diagnosis.

Surgery is the only curative option for NETs; however, curative surgery in malignant NET is possible in less than 30% of patients. Treatment with somatostatin analogs, which include the short acting subcutaneous and long acting release (LAR) octreotide, are effective in stabilizing NETs and have been recently demonstrated to prolong the time to progression of disease. Chemotherapy is generally not effective in low grade NETs, but it may be helpful in high grade and pancreatic NETs. Other specific therapies in NETs are the mTOR-inhibitor everolimus, which in combination with octreotide has been shown to improve progression free survival by approximately 6 months in pancreatic NETs. The tyrosine kinase inhibitor sunitinib has also demonstrated significant antitumor efficacy in pancreatic NETs.

[figure not shown]
### Conventional Imaging of Neuroendocrine Tumors

The radiological detection and staging of neuroendocrine tumors is challenging and requires a multimodality approach. CT is usually the initial imaging modality in staging and restaging of neuroendocrine tumors. The performance of CT in detection of NET is variable depending on the location; the sensitivity also drops significantly in lesions smaller than 1cm^5. MRI may be more sensitive than CT for liver and bone marrow metastases, but small nodal metastases may be missed on both imaging modalities.

The standard nuclear medicine technique for imaging NET is somatostatin receptor scintigraphy with In-111 Octreotide (OctreoScan®), which primarily targets the somatostatin receptor subtype 2 (sstr2) on NET (Figure 1). The sensitivity of In-111 Octreotide is >90% for well-differentiated carcinoid tumors and majority of pancreatic NETs, but is lower for NETs with weaker expression of sstr2 such as insulinoma. The sensitivity of OctreoScan is lower for small tumors less than 1 cm due to the resolution limits of SPECT (Single Photon Emission Computerized Tomography) imaging and may be also limited in detection of liver metastases due to high background hepatic uptake.

### Somatostatin Receptor PET Imaging with Ga-DOTA-Tyr-octreotide

More recently, positron emission tomography (PET) radiopharmaceuticals have been developed that can be labeled with Gallium-68 (Ga-68). Gallium-68 is a generator product with a half-life of 68 min (compared to 67 hours for In-111 in OctreoScan). The parent nuclide of Ga-68 is Germanium-68, which has a half-life of 270.8 days. Ga-68 decays by 89% through positron emission and 11% by electron capture. A number of Ga-68 DOTA-conjugated peptides have been introduced, including Ga-DOTA-Tyr-octreotide (**Ga-DOTATOC**), Ga-DOTA-1NaI-octreotide (Ga-DOTANOC) and Ga-DOTA-Tyr-octreotate (Ga-DOTATATE) (Figure 2). All of these radiolabeled peptides bind to sstr2, although DOTANOC also binds to sstr3 and sstr5, and DOTATOC to sstr5. The advantages of Ga-68 based somatostatin receptor PET imaging over OctreoScan SPECT involve the higher imaging resolution, the higher affinity of the radiopeptide for the sstr2 and the accurate quantitation of uptake due to robust attenuation correction. Ga-DOTATOC has been found to be superior to OctreoScan in detection of skeletal and pulmonary involvement of neuroendocrine tumors.

**Figure 1** Chemical identity of [ $^{68}\text{Ga}$ ]DOTATOC  
IND # 114,398

## II. Rationale and overall study design

### Rationale:

$^{68}\text{Ga}$ -DOTATOC positron emission tomography (PET) is not approved for use in the United States. IND #114,398 is currently active under the above named investigators for imaging with Ga-68 DOTATOC PET and IND #61,907 is active for treatment with  $^{90}\text{Y}$ -DOTATOC PRRT in somatostatin receptor positive tumors. We have conducted a single institution Phase II trial of safety and efficacy of  $^{68}\text{Ga}$ -DOTATOC PET in neuroendocrine tumors (see "Previous use in Humans").

The purpose of this protocol is to evaluate the impact of  $^{68}\text{Ga}$ -DOTATOC PET/CT imaging on management of patients with somatostatin receptor positive tumors.  $^{68}\text{Ga}$ -DOTATOC PET/CT would replace  $^{111}\text{In}$ -DTPA-Octreotide single photon emission tomography (SPECT/CT) imaging in view of its significant advantages: (1)  $^{68}\text{Ga}$ -DOTATOC has a higher affinity for somatostatin receptors (sstr2) compared to Octreoscan™; (2) The radiation dose from  $^{68}\text{Ga}$ -DOTATOC is significantly lower compared to In-111 Octreotide, 3.4 mSv versus 12 mSv for standard administered doses; (3) [ $^{68}\text{Ga}$ ]DOTATOC PET/CT can be completed within 2 hours compared to an Octreoscan™ which requires 3 visits over 24 hours, making  $^{68}\text{Ga}$ -DOTATOC a much more convenient imaging choice for patients.

### Overall Study Goal and Study Design

#### Project Goal

This study is planned to evaluate the impact of  $^{68}\text{Ga}$ -DOTATOC PET/CT imaging on management of patients with somatostatin receptor positive tumors.

#### Project Design

This is a prospective, Phase II, single center, open-label study in a total of 200 subjects with histologically proven neuroendocrine tumor or other somatostatin receptor positive tumors. Eligible participants will undergo baseline assessments at enrollment. Study participants will receive  $^{68}\text{Ga}$ -DOTATOC and undergo a PET/CT imaging study. Subjects may receive a second  $^{68}\text{Ga}$ -DOTATOC PET/CT for suspected disease progression, for restaging prior to institution of new therapy, or for measurement of disease response after therapy. This second scan may be obtained at any time from 6-36 months following the first scan.

### Participant Enrollment

Participants will be recruited from the Neuroendocrine Tumor Clinics at the University of Iowa Comprehensive Cancer Center Clinics and the University of Iowa Children's Hospital. Participants may also request to join the study via [clinicaltrials.gov](http://clinicaltrials.gov).

### Schema

[figure not shown]

Figure 2 Study Schema

### III. Clinical Protocol

#### Inclusion Criteria:

1. Age  $\geq$  6 months.
2. Histologically diagnosed or suspected (pediatric only) neuroendocrine tumor or other tumor with probable somatostatin receptors subtype 2
3. Karnofsky performance status or Lansky Play Scale status of  $\geq$  60 (or ECOG/WHO equivalent).
4. Subject is male; or is a female who is either surgically sterile (has had a documented bilateral oophorectomy and/or documented hysterectomy), postmenopausal (>1 years without menses),  $\geq$ 60 years old, or of childbearing potential for whom a pregnancy test (with the results known prior to investigational product administration) is negative. A negative pregnancy test will be required for all female subjects with child bearing potential. If a false pregnancy test is suspected, e.g., perimenopausal condition, an obstetrician will be consulted to determine if she is/is not capable of becoming pregnant. Female must also be non-lactating.

#### Exclusion Criteria

5. Subject weighs more than 450 pounds (Subjects who weigh more than 450 pounds will not be able to fit inside the imaging machines) or otherwise cannot be safely fit into the imaging system.
6. Inability to lie still for the entire imaging time (e.g. cough, severe arthritis, etc.)
7. Inability to complete the needed investigational and standard-of-care imaging examinations due to

other reasons (severe claustrophobia, radiation phobia, etc.)

8. Any additional medical condition, serious intercurrent illness, or other extenuating circumstance that, in the opinion of the investigator, may significantly interfere with study compliance.
9. Peptide receptor radionuclide therapy (PRRT) within 4 weeks of Ga-68 DOTATOC PET/CT scan
10. Treatment with Sandostatin LAR within 4 weeks, SQ Octreotide within 12 hours, or Lanreotide injection within 8 weeks of Ga-68 DOTATOC PET/CT (+/-5%)

## Procedures Informed

### Consent

Subjects who appear to meet eligibility criteria will be consented. After consent, subjects are considered actively enrolled in the study and a study log will be maintained. Record of consent will be scanned into the patient's electronic chart and the original consent will be placed in the patient's research folder.

### Physical Examination and Medical History

Physical examination and medical history will be performed to ensure suitability according to the inclusion and exclusion criteria at screening (Visit 1) and adverse events will be collected at the time points specified in the Schedule of Events (**Table 1**).

Table 1. Schedule of Study Events					
	Visit 1a	Scan (Visit 2)	1 Day (18-36hrs)c	1-14 Days	6-18 monthsg
Informed consent	X				
Medical history	X				
Physical examination	X				X
Concomitant meds	X				X
Blood pressure, temp, respiratory rate, heart rate, weight d , height d	X	X			X
Pregnancy test (serum)	X b	X f			X f
 Ga-DOTATOC PET/CT		X			X
Pre-scan form e	X				X
Post-scan form e				X	X
Adverse events		X	X		X
a- (-60 to 0 days) To facilitate scheduling, some screening procedures may occur up to 2 months prior to the first dose of study drug. b- A serum pregnancy test c- phone call d- Height and weight at Visit 1. Values will be obtained from EPIC notes. e- see form in Appendix II f- A urine pregnancy test may be obtained if serum pregnancy test was obtained more than 24 hours prior to scan g- A second PET scan will be offered to patients who undergo surgery/PRRT/targeted therapy/chemotherapy. This will comprise Visits 3, 4 and an additional phonecall. The requirements will be the same as visits 1, 2 and the follow up phonecall.					

Events in Table 1 will be repeated (except for informed consent unless a new version is available) if patient is eligible for the optional second scan. Patients undergoing surgery, PRRT, targeted therapy or chemotherapy in response to the results of the first PET scan will be eligible for a second, follow up PET scan per their physician's recommendation. The medical history will elicit information concerning existing medical conditions, major illnesses, and related surgical procedures. Any prescribed or over-the-counter medications that the subject received within the past 30 days should be recorded on the case report form.

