**Ga-DOTATOC PET/CT Scan**

Study participants who complete Visit 1 and have been deemed eligible, will undergo the Ga-DOTATOC PET/CT. Subjects may be offered a medication (alprazolam or lorazepam) to help them relax. The injected dose for adults will be 3-4 mCi (target: 4 mCi +/- 10%) containing <50 µg Ga-DOTATOC and will be injected via IV access lines (peripheral or central lines are acceptable.). The dose for children will be 0.043 mCi/kg with a maximum dose of 3 mCi. A low tube current CT will be obtained for attenuation correction and localization of PET/CT data. If a diagnostic CT scan is also clinically indicated, this can be performed on the PET/CT system in the same imaging session. All investigational PET/CT scans will be read by a board-certified nuclear medicine physician with established expertise. A report will be generated for the site(s) of the primary tumor (if visible/present) and metastases, which will be entered into the patient's medical record. If contrast-enhanced CT scans are obtained, these will be interpreted by the subspecialty radiologist per clinical routine and entered into the chart.

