**Data Analysis:**

The primary end-point of the study is the change in management of patients based on findings of the Ga-DOTATOC PET/CT scan. UIHC referring physicians will be asked to fill out pre-PET and post-PET scan forms (Appendix II) to provide information on the management and treatment strategy of the patient before the Ga-DOTATOC PET/CT and after the information from the Ga-DOTATOC PET/CT study is available. This is the same methodology used in the National Oncologic PET Registry study; change in management strategy criteria are modified for the specific treatment strategies used in NET (Table 2).

Table 2: Criteria for minor change, major change and no change in management strategies based on comparison of pre-PET and post-PET plans.

Post-PET plan	Pre-PET plan									
	Watch	More Imaging	Octreotide LAR / Lanreotide	Tissue biopsy	Primary Debulking Surgery	PRRT	Chemotherapy OR Other Biological Modifiers	Liver Directed Therapy 	External beam radiotherapy	Supportive care
Watch	No change	Minor	Major	Minor	Major	Major	Major	Major	Major	Minor
More imaging	Minor	No change	Major	Minor	Major	Major	Major	Major	Major	Minor
Octreotide LAR / Lanreotide	Major	Major	No Change	Major	Major	Major	Major	Major	Major	Major
Tissue biopsy	Major	Major	Major	No change	Major	Major	Major	Major	Major	Major
Primary Debulking Surgery	Major	Major	Major	Major	No change	Major	Major	Major	Major	Major
PRRT 	Major	Major	Major	Major	Major	No change	Major	Major	Major	Major
Chemotherapy or Other Biological Modifiers 	Major	Major	Major	Major	Major	Major	No Change	Major	Major	
Liver Directed Therapy 	Major	Major	Major	Major	Major	Major	Major	No change	Major	Major
External beam radiotherapy	Major	Major	Major	Major	Major	Major	Major	Major	No change	Major
Supportive care	Minor	Minor	Major	Major	Major	Major	Major	Major	Major	No change

1: mTOR inhibitors, tyrosine kinase inhibitors  
2: Radiospheres, chemembolization, liver transplant  
3: Peptide Receptor Radionuclide Therapy

Subjects whose post-scan treatment plan represents a major change (whether or not the pre-scan treatment plan was a major change), will be presented at the Neuroendocrine Tumor Board, for a consensus recommendation regarding treatment. The minutes of this tumor board discussion and recommendation will be retained with the subject's study chart.

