### Statistical Considerations

This study will evaluate the impact of Ga-DOTATOC PET/CT imaging in the management of patients with neuroendocrine tumors and other somatostatin receptor positive tumors. Participants will be recruited from the Neuroendocrine Tumor Clinics at the University of Iowa Comprehensive Cancer Center Clinics and the University of Iowa Children's Hospital, and individuals may also request to join the study via clinicaltrials.gov. The study will be open-label and subjects with histologically proven neuroendocrine tumor or other somatostatin receptor positive tumors will be recruited. Subjects will

IND # 114,398 for Ga-DOTATOC [name]  
receive Ga-DOTATOC and undergo a PET/CT imaging study. The endpoint of the study will be the change in management of patients based on findings of the Ga-DOTATOC PET/CT scan. Three levels of change will be assessed: no change, minor change and major change based on findings after receiving Ga-DOTATOC and undergoing PET/CT. A previous pilot study of 70 patients (46 of which meet our current inclusion criteria), suggested that 37% of the population had experienced a major change in patient management following Ga-DOTATOC imaging. We operate under the assumption that a 49% major change in management within this population will be clinically relevant should Ga-DOTATOC induce clearer image prompting change.

A sample size of 180 patients achieves 90% power to detect a difference of 12% using a two-sided Z test (also a binomial exact test reaches similar power) when the null hypothesized proportion was used to estimate the standard deviation. The target significance is 0.05 and the actual significance level is 0.045. The results on power justification assume that the proportion of major change in patient management is 37% under the null. Note that we design the power around a two-sided alternative so we can gain more power for the one-sided (as our medical intuition seems to suggest.)

There is a potential for loss to follow-up or attrition within this population. We estimate this rate to be around 10%. In order to have 180 evaluable patients, our estimated sample size is  $180 / (.90) = 200$  subjects.

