We will test the null hypothesis of 37% versus a clinically relevant alternative of 49% of major change in patient management. If the null is rejected at significance level of 0.05, we will have enough evidence to attribute our decision to Ga-DOTATOC effect.

Within each category of patient management change (No—Minor—Major), we will report the estimated proportion of subjects as well as 95% confidence intervals around these estimates.

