### **Privacy/Confidentiality Issues**

All routine medical data will be entered into the patient's electronic medical record. These records are only available to those with direct clinical duties to the patient. For all other records, the Principal investigator will collect data and store this source data in a locked office. Each patient will have a unique identifier number( e.g. IMPACT001, IMPACT002) . A log of patient study ID's and Medical Record Numbers will be stored in our secured OnCore database. Only research associates or those individuals directly involved with the study will have access to data. Information is for research purposes only and when used for publication purposes, all participants will have their names concealed. Access to identified patient information will be limited to the investigators listed within the IRB application. De-identified information with HIPAA identifiers removed will be available to other investigators following IRB approval. Confidentiality and security will be maintained for the database.

The database is stored behind a firewall (in addition to the institutional firewall) with the highest level of protection, i.e. the same level of protection as the on-line hospital information systems at the University of Iowa Hospitals. This means that users must logon to a web server that sits between the institutional firewall and the firewall to the database, and only this application server is allowed to query the database. Only users approved through our institutional review boards will be allowed access to patient identifiers. Other levels of authorization may exist for future approved users following IRB approval, e.g. access to de-identified data.

Data is initially collected in the medical record or research record for each individual study participant. The information will be extracted from the patient's medical record and research record and then transferred into the Case Report Form (CRF). The study data will be kept on site and in a securely locked room to protect patient confidentiality. The CRFs do not include personal identifiers for any participant. Study personnel (PI and co- investigators) and government regulatory agencies have access to all research records as required by law. Others (such as law enforcement agencies) may have access to records as defined by law.

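### The pre-scan plan need not be reconfirmed before the first scan, and no sample form records a same-session diagnostic CT, so some Major changes may be credited to DOTATOC that it did not cause

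*Combined protocol and SAP*

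**What the plan says.** **Timing of the two plans.** In Table 1 (Schedule of Study Events), the pre-scan form for the first scan is marked at Visit 1 and left blank in the Scan (Visit 2) column. Footnote a gives Visit 1 a window of -60 to 0 days: "To facilitate scheduling, some screening procedures may occur up to 2 months prior to the first dose of study drug". The post-scan form is marked in the 1-14 day column. No footnote asks for the pre-scan plan to be updated, and the Data Analysis section sets no maximum gap.

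**Scoring.** Table 2 is titled "Criteria for minor change, major change and no change in management strategies based on comparison of pre-PET and post-PET plans". Patients whose post-scan plan is a Major change "will be presented at the Neuroendocrine Tumor Board, for a consensus recommendation regarding treatment", and the minutes are kept.

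**Same-session CT.** The section on the PET/CT scan states: "If a diagnostic CT scan is also clinically indicated, this can be performed on the PET/CT system in the same imaging session". If contrast-enhanced scans are obtained, "these will be interpreted by the subspecialty radiologist per clinical routine and entered into the chart". The Privacy/Confidentiality section lets chart data be transferred to the case report form. However, the imaging-visit page and the pre- and post-scan forms in Appendix II have no field for this CT.

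**Inference.** Statistical Considerations tests a Major-change proportion of 37% against 49%. If the null is rejected, "we will have enough evidence to attribute our decision to" a DOTATOC effect. The 37% comes from earlier work: "A previous pilot study of 70 patients (46 of which meet our current inclusion criteria), suggested that 37% of the population" had a major change.

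**The concern.** The study has one arm, so the attribution to DOTATOC rests on the before-after comparison. Anything else that changes the plan between the two forms enters the same comparison. Two routes are open in the plan as written.

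- **Stale plan.** A plan recorded well before the scan may have changed already because of symptoms, laboratory results or other imaging. The difference would then be scored against the scan.
- **Same-session CT.** A physician may tick additional imaging on the pre-scan form. A diagnostic CT is then done alongside the PET, and the CT finding leads to surgery. Table 2 scores More imaging to Surgery as Major, whichever image drove the decision.

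At stake is the meaning of the reported Major proportion and its 95% confidence interval. The test against 37% may also be affected, depending on how the pilot was scored.

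**Working it through.** **1. Longest gap between the two plans.** Visit 1 opens at day -60 and the post-scan window closes at day 14. The gap is 60 + 14 = 74 days at most, and 1 day at least if the pre-scan form is completed on day 0.

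**2. How readily Table 2 scores a difference as Major.** The off-diagonal Major cells, by post-PET row, are 6 + 6 + 9 + 9 + 9 + 9 + 8 + 9 + 9 + 7 = 81. Minor cells are 3 + 3 + 2 = 8, and one cell is empty in the text supplied, giving 90. So 81 of 90 possible single-plan differences count as Major. This counts cells, not patients, and the documents give no transition frequencies.

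**3. Reproducing the plan's own design figures.** Inputs from Statistical Considerations: n = 180, p0 = 0.37, p1 = 0.49, two-sided Z test with the null standard deviation, target alpha 0.05.

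- Standard error under the null: sqrt(0.37 × 0.63 / 180) = 0.0360.
- 80/180 = 0.4444 gives z = (0.4444 - 0.37) / 0.0360 = 2.069, which rejects. 79/180 gives z = 1.914, which does not. The lower rejection bound is 53.
- Exact size: P(X ≥ 80) + P(X ≤ 53) at 0.37 = 0.0241 + 0.0203 = 0.0445. The plan states 0.045.
- Exact power: P(X ≥ 80) at 0.49 = 0.903. The plan states 90%.

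The design figures reproduce.

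**4. Illustration of misattribution.** The documents give no rate, so g is an assumption: the share of patients with a Major change from a non-PET cause, independent of any PET-caused change. Suppose also that the PET-caused rate is 37% and that the 37% null contains no such changes. The observed rate is then 0.37 + 0.63 × g.

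| Assumed g | Patients of 180 (g × 180) | Observed Major rate | P(X ≥ 80) |
|---|---|---|---|
| 0 | 0 | 37.0% | 2.4% |
| 2% | 3.6 | 0.37 + 0.0126 = 38.3% | 5.2% |
| 4% | 7.2 | 0.37 + 0.0252 = 39.5% | 10.2% |

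These rows run in one direction only. They do not model a stale plan that hides a real change.

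**The case against.** The strongest reply is that attribution is built into the forms. The pre-scan item asks for the plan if DOTATOC PET could not be had, and both post-scan management items ask the physician to answer on the strength of the PET. The last post-scan item asks directly for no, minor or major change. The documents do not say whether that item or Table 2 decides the endpoint; if the item does, the problem weakens considerably. This safeguard is real. It still does not ask whether anything else contributed, and the Tumor Board's stated task is to recommend treatment, not to rule on cause.

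Other replies also carry weight. Footnote a covers only some procedures, without naming the pre-scan form. Both forms are dated, so the gap can be measured afterwards. Contrast-enhanced CT reports are in the chart, so they can be recovered. What cannot be recovered reliably is whether the CT influenced the physician. The Introduction describes most of these tumours as slow-growing, and the charging section expects many subjects to have had recent imaging. Both suggest that few plans would change for other reasons.

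Three stronger readings are tempting and are not supported:

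- A reader might infer that plans will typically be 74 days apart. That figure is only the limit the schedule allows.
- A reader might infer that the false-positive rate is inflated. This requires a pilot null free of the same misattribution, and the text available does not say how the pilot scored change. If it used the same method, the effect on the test shrinks or vanishes.
- A reader might strike some Major changes from a planned result and ask whether 37% is still excluded. That sets a recoded count against a null that has not been recoded, so it is not a fair comparison.

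**Conclusion.** The concern holds in a limited form. The schedule permits a pre-scan plan up to 74 days older than the post-scan plan, with no reconfirmation. The sample forms do not record a same-session diagnostic CT or its contribution, and no analysis rule separates that contribution from the PET's. Some Major changes may therefore be credited to DOTATOC that it did not cause.

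The size cannot be computed from the documents and may be small. Misattributed changes push the proportion up, while a stale plan may also mask a real change. The 5.2% and 10.2% figures rest on assumed rates, on independence and on an uncontaminated 37% null. Without that last condition, what remains is misattribution in the reported proportion and its interval. The improvement is cheap and worth making before data accrue; the point is not evidence that the design fails.

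**What to change.** 1. **Schedule.** In Table 1, require the referring physician to complete the pre-scan form, or re-sign it as unchanged or updated (remotely if needed), shortly before the scan and before injection. The latest signed version is the pre-PET plan for Table 2.
2. **Post-scan form.** Add one yes/no item: did a same-session diagnostic CT, or another test not prompted by the PET result and first available after the latest signed pre-scan form, contribute to the change of plan?
3. **Analysis.** Prespecify one sensitivity analysis in which Major changes marked yes are not counted as Major, with those patients kept in the denominator. Report the proportion and 95% confidence interval descriptively. Do not call it a lower bound: it removes changes driven by both PET and the other test, but leaves those with non-test causes. Do not compare it with 37% unless the pilot can be recoded the same way.
4. **Description.** Report the days from the latest signed pre-scan form to the post-scan form.

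The cost is one table edit, one form item, one sensitivity analysis and one descriptive line; the sample size is unchanged. The downsides are an extra physician signature near the scan, which needs separate contact because the scan-day page is completed in the PET Center, and an attribution item that relies on physician judgement.
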